14.1 Data Collection and Management Responsibilities

Primary data collection from participants in the RCT will occur by approved, trained study RAs at the study EDs. Data collection will occur using REDCap on secure tablet computers (e.g., iPads), which will be password protected. Access to REDCap will only be granted to approved study personnel, each of whom will have a unique user ID and password to be used when collecting data. REDCap permissions and functionality will be restricted for RAs so that they do not have the ability to delete records or change forms. In addition to these protections, REDCap has other functionality that will ensure data collected are complete and reliable, including data entry field limitations and forced responses to indicated questions. REDCap also automatically maintains an audit log of all REDCap activity, including any changes made to records and who has made them. All information entered into REDCap is automatically saved in the NYULH REDCap project, accessible only to approved study personnel. All study sites will use the same approved NYULH REDCap project. For QA monitoring and data analysis, REDCap data will be downloaded in the form of Excel and/or statistical programming software files. These files will be password protected and saved in secure NYULH IT-managed network drive accessible only to the PI, PM, and any other approved personnel. Electronic consent forms will also be stored on REDCap. There are no paper questionnaires or other forms that will be saved from the RCT visits.

The PI and PM will monitor data collection regularly via the QA/QC procedures outlined in Section 12. Further, all RAs will receive standard training in study procedures and will complete supervised shifts until they are fully competent in all study data collection. The PM and PI will be available in real-time to answer any RA's questions about data collection. Further, weekly study team meetings will be used to continually reinforce standards of good data collection and management.

The primary outcome will be ascertained in part by data abstraction from a variety of administrative health databases, including primarily the Regional Health Information System (RHIO) databases, also called Bronx RHIO and Healthix. We will also use individual health system electronic medical records (which may be accessed through data warehouses or directly for sites participating in the study). Other sources of administrative data that may be used if data is incomplete in the aforementioned sources include Medicaid and SPARCS. Study participants will provide informed consent for the study investigators to access information about them in these datasets. Approval and use of these datasets will follow defined procedures for research specific to each source dataset. Data abstraction will occur directly into a REDCap secure data collection form. Data will only be accessed for study participants. RHIOs may request and receive from the study investigators a list of participants (including personally identifying information) in the study, to allow them to conduct a data match with RHIO data and share results with the investigators. All appropriate and applicable permissions will be obtained from the holders of administrative data outside the study sites prior to their use for research (e.g., completion of RHIO application for research use), and DUAs will be executed prior to data sharing as necessary.

Additionally, DOHMH collects Relay program data which it maintains in a programmatic database known as Maven. All data entered into Maven are stored in a secure, password protected, SQL Server Database on the DOHMH servers. Access is restricted to approved DOHMH staff and restricted access will be granted to approved NYU study team members. NYU study team members will enter limited participant information into Maven (see Attachment) for the following purposes: (1) participant identifying information (e.g., name, date of birth, race/ethnicity) so that DOHMH can match study participants to death records to allow ascertainment of the primary study outcome (Section 3.1) and also tracking for purposes of the study stopping rule (Section 8.7); (2) participant contact information so that the Relay program can contact SDC arm participants after the study is over to offer Relay services (see Section 6.1), and (3) information on NYU RA distribution of naloxone kits to SDC arm participants, as DOHMH is providing the naloxone kits to NYU and is legally required to monitor their distribution. Study participants will provide informed consent for the NYU study team to share this information about them with DOHMH.

CONFIDENTIAL

This material is the property of the NYU School of Medicine and NYU Langone Health. Do not disclose or use except as authorized in writing by the study sponsor
Behavioral Intervention Template Version: 11 January 2019

DOHMH also keeps data on overdose and other deaths in NYC and has other administrative health data that we may use for this study. For any data to be shared by DOHMH with the NYU study team, we will execute a Data Use Agreement (DUA) and/or Memorandum of Understanding (MOU) with DOHMH to govern data use and sharing prior to access or use of any of these data.

We will be providing a list of participant names and birthdates of people who have participated in the SDC arm to the Relay hotline call center. The call center will not be provided with any other participant information. Using a secure, password protected file transfer portal that only NYU and the Relay hotline call center will have access to, the PM or RC will transfer the list of participant names. This information will be provided securely to the Relay hotline call center because there is not a study RA on call 24/7 and therefore the call center needs an alternate way of knowing when a patient for whom Relay is activated is in the study SDC arm meaning a Wellness Advocate should not be dispatched to visit the patient (because this would cause crossover between study arms). This will only be relevant in the rare instances for which a study participant in the SDC arm has a repeat overdose visit to an emergency department participating in the study and the Relay hotline is called. In these cases a study RA will conduct an unscheduled visit or follow-up visit as appropriate (see Section 7.3) in the ED once available (if the participant remains in the ED) or will attempt to follow up by phone. The Relay hotline call center activities related to this study follow a comprehensive data privacy and security agreement with the NYC Department of Health and Mental Hygiene, which specify data security procedures, rules against data sharing, and other protections for privacy of the data. The Relay hotline call center will delete all participant lists after completion of the study follow-up period, one year after enrollment of the last study participant.

The study PIs will have ultimate responsibility for overseeing data collection and management. The PIs are responsible for ensuring the accuracy, completeness, legibility, and timeliness of the data reported.

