2.3.2 Known Potential Benefits

Participants are not expected to benefit from the study directly, as they will not be receiving new interventions not otherwise available to them in the ED. We expect that overdose education and provision of naloxone (in both conditions) will reduce future opioid-related adverse events among patients presenting with nonfatal OD; of note, OEND is generally standard care at study sites already, but for the study we will ensure it occurs for all study participants. The Relay peer navigator intervention has the potential to provide additional benefit to patients, but its effectiveness has not been established. The community at large, including patients and providers, stands to benefit from the knowledge gained from this study about reducing OD fatalities, and barriers and facilitators to OD prevention programs. The results of this study are critical to advancing science around preventing OD fatalities, informing the allocation of resources in NYC, and informing other jurisdictions as they scale up opioid OD prevention efforts.

CONFIDENTIAL

This material is the property of the NYU School of Medicine and NYU Langone Health. Do not disclose or use except as authorized in writing by the study sponsor
Behavioral Intervention Template Version: 11 January 2019

3 Objectives and Purpose

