6.1 Study Behavioral or Social Intervention(s) Description

Individuals assigned to the Relay arm will receive the Relay peer navigator-led intervention. The Relay program is designed and administrated by DOHMH; the NYULH study investigators do not have control over Relay program operations. DOHMH may modify the intervention components or administration. The Relay program model by design is tailored to patient needs and therefore exact intervention components delivered to individual Relay participants may differ; the study investigators will monitor but will not attempt to change intervention components delivered. The present study is adding 1) random assignment and 2) evaluation procedures to investigate the implementation and effectiveness of Relay.

DOHMH's Relay program comprises two components, both conducted by the peer navigator.

The first component is conducted in the ED after the patient has been medically stabilized and consists of 1) engagement and support, to build relationships and foster trust; 2) tailored overdose prevention information and risk reduction counseling; 3) training on naloxone and provision of a naloxone kit if one has not yet been provided by the ED (or additional kits if needed); and 4) offer to follow up with the individual for up to 90 days to provide ongoing support and linkage to services, including opioid treatment programs. Throughout this component, the peer navigator serves as a positive role model and seeks to reduce stigma by highlighting shared lived experiences. Patients may be uncomfortable, distressed, and anxious to be discharged; peer navigators address these concerns in a number of ways. Consistent with the motivational interviewing approach, peer navigators support patients' autonomy and 'roll with resistance.' Engagement is fostered through tangible support (obtaining snacks, getting answers to questions) and instrumental (social) support. Tailored OD prevention education and training on naloxone is provided when patients are comfortable and engaged, and takes a motivational interviewing approach. The peer navigator obtains the patient's contact information and makes plans to follow up with them.

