Enrollment and informed consent. RAs will enroll and obtain consent from eligible patients for participation in the research activities. The RA will explain the study procedures and incentive schedule, answer any questions, and offer enrollment. Patients will be informed that the decision to participate in the research is voluntary and will not affect the medical care they receive from the ED. If the patient is willing to participate and signs the informed consent form, only then will study staff commence collecting additional information. The informed consent process will be conducted in-person on a study iPad using REDCap (using electronic consent/signature). The participant will be given a paper or e-mailed copy (through REDCap) of the informed consent form and key information sheet. If the patient declines to participate in the study, the RA will call the Relay peer navigator to inform him/her of the patient who has declined to participate in the study but who could potentially receive Relay services (apart from the study, as part of standard DOHMH Relay practice).

Randomization. Patients who meet eligibility criteria and agree to participate in the study will be randomized to the SDC vs. Relay arm. The RA will use an electronic system (REDCap) to create a random assignment to a treatment arm. Randomization uses a 1:1 ratio and is stratified by site; permuted blocks with variable blocks of size 4 and 6 will be used to maintain balance over time and prevent prediction of assignment by the RA. Upon randomization, the RA will immediately inform the participant of the treatment arm assigned. For Relay arm participants, the RA will then inform the Relay peer navigator by phone. If the participant is assigned to the Relay arm, the peer navigator will generally arrive at the ED within 30 minutes.

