Additional unscheduled visits: Participants in both the SDC and Relay intervention arms will be given a study phone number and may reach out to the RA at any point during the study period. All such unscheduled encounters will be documented by the RA using a designated study form. RAs will also attempt to contact study participants between visits to confirm contact information and intermediate and final study appointment information. RAs will mail participants appointment reminder letters. If study staff is still unable to reach the participant after multiple attempts of contact, and the participant has given permission to do so, RAs may mail a letter to the participant's contacts asking to help our study staff get in contact with the participant. Additionally, RAs will mail participants a thank you card and a holiday card when applicable. Finally, if participants present to the ED after a repeat opioid OD in which the Relay hotline is activated, RAs will attempt to visit the participant in the ED if possible (e.g., if an RA is available) to confirm contact information and visit appointments (or to conduct one of the scheduled intermediate or final study visits if within the appropriate time window).

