Attachment A

Schedule of Events

| Activity | Baseline | 1 Month Visit | 3 Month Visit | Interim Contacts | 6 Month Visit | Qualitative Interviews | 12-Month Outcome Abstraction |
|--|----------|---------------|---------------|------------------|---------------|------------------------|------------------------------|
| Screening | | | | | | | |
| ED provider calls Relay hotline | X | | | | | | |
| Assignment of RA | X | | | | | | |
| Screening for eligibility | X | | | | | | |
| Informed consent process | X | | | | X | | |
| Primary Study Procedures | | | | | | | |
| Randomization | X | | | | | | |
| Participant questionnaire | X | X | X | X | X | X | |
| Participant information form | X | | | | | | |
| Locator form | X | | | | | | |
| Relay intervention or SDC* | X | | | | | | |
| Exit survey | X | | | | | | |
| Semi-structured interview | | | | | X | X | |
| Administrative data extraction | | | | | | X | |
| Additional Participant Contacts | | | | | | | |
| Mail "Thank you" card (within week following baseline visit) | | | | X | | | |
| Mail "Holiday" card (if applicable) | | | | X | | | |
| Mail "Appointment reminder" cards (if applicable) | | | | X | | | |
| Confirm locator form information | | X | X | X | X | X | |
| Confirm next study appointment | X | X | X | X | X | X | |
| Additional Study Procedures | | | | | | | |
| Give study contact card | X | | | | | | |
| Reimbursement and Greenphire ClinCard FAQ (if applicable) | X | X | X | X | X | X | |

CONFIDENTIAL

This material is the property of the NYU School of Medicine and Langone Health. Do not disclose or use except as authorized in writing by the study sponsor

CONFIDENTIAL

This material is the property of the NYU School of Medicine and Langone Health. Do not disclose or use except as authorized in writing
by the study sponsor

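### When an SDC participant returns to a study ED with an overdose, the Relay peer is withheld and the protocol gives the replacing RA contact no naloxone task

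*Combined protocol and SAP*

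**What the plan says.** Section 14.1 gives the hotline call center the names and birthdates of SDC participants, because RA cover is not round the clock. If one of them has a repeat overdose visit at a study ED and the hotline is called, the list identifies the patient as SDC, "meaning a Wellness Advocate should not be dispatched to visit the patient (because this would cause crossover between study arms". (Wellness Advocate is that section's term for the Relay peer.) The replacement is: "In these cases a study RA will conduct an unscheduled visit or follow-up visit as appropriate (see Section 7.3) in the ED once available". This applies if the patient is still there; otherwise the RA tries by phone.

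Section 7.3.5 gives the purpose of an RA visit at a repeat overdose: "to confirm contact information and visit appointments (or to conduct one of the scheduled intermediate or final study visits".

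Section 6.1 lists among the peer's ED tasks "training on naloxone and provision of a naloxone kit if one has not yet been provided by the ED (or additional kits if needed".

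Section 2.3.2 sets out the investigators' view of OEND: "We expect that overdose education and provision of naloxone (in both conditions) will reduce future opioid-related adverse events among patients presenting with nonfatal OD". It adds: "OEND is generally standard care at study sites already, but for the study we will ensure it occurs for all study participants".

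**The concern.** The no-dispatch rule is a sensible way to protect the contrast between arms, and the question of whether peer navigation works is properly left to the trial. OEND is different. The protocol expects it to help in both arms, makes it the SDC minimum, and promises it to every participant because it is only generally, not always, standard at the sites.

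At the index visit the promise has a mechanism: an RA who supplies OEND and an exit survey that confirms it. At a repeat overdose the study removes the peer, who would have filled any gap left by the ED, and the written RA task does not take over that function. The study itself introduces this difference. Under Section 7.3.1 a patient who declines the trial is referred to the peer as someone "who could potentially receive Relay services (apart from the study, as part of standard DOHMH Relay practice". The point matters because it falls just after another overdose, when kits given at index may have been used or lost.

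**Working it through.** The protocol states no figure on this point, so the check is mainly a comparison of texts.

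**Who checks naloxone at the index visit?** In the SDC arm the RA ensures OEND and gives 1-2 kits if ED staff have given none (Sections 6.1 and 7.3.1). The exit survey requires the RA to tick that it was received (Sections 6.1.2 and 10.4.5). In the Relay arm the peer does this (Section 6.1).

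**Who checks at a repeat overdose visit by an SDC participant?**
- The peer: barred by Section 14.1.
- The RA: attends when available or phones (Section 14.1). The stated tasks are contact details, appointments or a due interview (Section 7.3.5). Naloxone is not among them.
- ED staff: may give naloxone under site protocols. Section 6.1 says services vary by site and that the investigators will not try to influence them. Discharge hard stops are listed as one kind of site initiative, not as present at every site.
- The participant: may phone Relay, but Section 6.1 expects few to do so.

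No section supplied names a study role responsible for the check.

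**Does another rule fill the gap?** Section 7.3.1 has the RA call the peer for patients who are not eligible for the study. A returning SDC participant is ineligible because already enrolled (Section 5.2.1), so read literally this would bring the peer back. Section 14.1 is the specific rule for this situation and forbids it, so the general rule cannot be relied on.

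**Scale.**
- SDC participants: 350 / 2 = 175.
- Section 2.1 cites about 20% with an overdose in 12 months in another ED trial. 175 x 0.20 = 35 people. Over an assumed 10% to 30%: 175 x 0.10 = 17.5 and 175 x 0.30 = 52.5, or about 18 to 53.
- These are people with any overdose. The affected group is the subset who return to a study ED, have the hotline called, and are not given naloxone by the ED. The documents give neither the share who return with a hotline call nor the share the ED misses.
- The planning rate in Section 10.5 gives 175 x 2 = 350 to 175 x 3 = 525 events a year in SDC. It counts other substance use visits and events outside study EDs, so it is no more than a loose ceiling on visits.

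The calculation therefore stops at the size of the pool. Section 14.1 itself calls these instances rare.

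**The case against.** **Naloxone is not withheld.** The peer is a secondary source, giving a kit only if the ED has not or if more are needed. The treating ED keeps its full range of services, SDC participants receive OEND at index, and they can phone Relay at any time. This stands, and it limits the point to a missing backstop. The same could be said of the index visit, however, where the protocol still adds an RA check.

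**The duty may not be confined to baseline.** Sections 2.3.2, 6.1, 7.1 and 7.1.1 state it without naming a visit. The schedule in Attachment A marks "Relay intervention or SDC" once, at baseline, but that proves little: Relay itself runs for up to 90 days, and the table is damaged in extraction. Baseline remains the likelier reading, because the explicit procedure and its check are written there.

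**Other documents may cover it.** RA procedures are deferred to the SOP/MOP, and the Interim Contact Form (Attachment N) was not available. If either contains the step, a cross-reference is enough.

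**Safety is monitored.** The Section 8.7 stopping rule looks for excess overdose deaths in SDC twice a year, and naloxone possession is an exploratory outcome. Neither prompts action for an individual after a repeat overdose.

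**Stronger readings the documents do not support.**
- A reader might infer that the trial denies naloxone to the control arm. The sources just listed rule that out.
- A reader might put a number on those who leave without naloxone. That needs assumed shares for return with a hotline call and for ED omission, and neither has a basis in the text.
- A reader might attach the 10% one-year mortality in Section 2.1. That is overall mortality after a naloxone-reversed overdose, not risk from a missing kit.
- A reader might conclude that participants are misinformed, since Section 13.3.2 says taking part does not affect other services. Whether Relay dispatch is an other service is arguable, and the consent pages are not available.

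**Conclusion.** The point holds as a gap in a safety backstop. A rule added by the study removes the peer who would have checked for naloxone, and the protocol text gives the replacing RA contact no such check, despite the undertaking in Section 2.3.2. Those at risk are a subset of about 175 SDC participants, probably few; the documents do not allow a count. The conclusion assumes that the SOP/MOP and the Interim Contact Form do not already contain the step, and that the OEND duty is read as a baseline procedure. It does not depend on whether Relay works, and it does not touch the validity of the primary analysis. It is a modest change worth making because it concerns patient safety and is cheap.

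**What to change.** Add to Sections 7.3.5 and 14.1 wording such as: *At any return-overdose contact with an SDC participant, in the ED or by phone if no RA could attend, the RA confirms that overdose education and a naloxone kit were received, supplies or arranges them if not, and records this on the Interim Contact Form. Kits distributed are logged in Maven as at baseline.*

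The call center should not tell the clinician that the patient is in the SDC arm or ask for OEND. That could reveal the allocation, might affect how visits are recorded for the primary outcome, and would prompt site care that Section 6.1 says the investigators will not influence. If a message is wanted, limit it to a neutral statement that no peer is available; DOHMH would have to agree, since it runs Relay. When no RA attends, the phone check comes after discharge, so the fix narrows the gap without closing it entirely.

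The cost is a few more kits, one form item and an amendment. RAs already give OEND to SDC participants from DOHMH-supplied kits. The change delivers only the minimum that defines the SDC arm, with no peer contact, so it adds no crossover and leaves endpoints and sample size as they are.

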This material is the property of the NYU School of Medicine and NYU Langone Health. Do not disclose or use except as authorized in writing by the study sponsor

Behavioral Intervention Template Version: 11 January 2019

on the locator form (for whom participants have given our consent to contact). If these tracking methods are unsuccessful, we will initiate systems-level tracking. At enrollment, participants will have been asked to list agencies with which they have contact, and we will send a letter or flyer to each of these agencies requesting that they forward the enclosed letter to the participant's most current address. Additionally, we will use free systems-level tracking methods commonly used to locate participants in longitudinal studies. These include searching web-based phone and address directories, as well as criminal justice directories. In some cases we will attempt place-based tracking, canvassing locations where the participant reports often spending time. Further, we will monitor ED visits to study hospitals made by patients subsequent to the baseline visit, which may present an opportunity for performing follow-up visits. This monitoring will occur via Epic track boards and alerts provided to the study team via a secure and password protected online portal by the HealthIx RHIO (see Section 14.1).

3. Compensation. We will reimburse participants for their time completing study activities, as described in more detail in the sections that follow.

4. Reminders. Beginning approximately two weeks before each follow-up assessment is due, study staff will begin reaching out to participants. Staff will make multiple attempts at different times of day and days of the week, and via different contact modalities, to reach participants. Staff will conduct multiple contact attempts for participants who do not complete scheduled assessments; windows before and after the follow-up assessment due date will be allowed to complete the assessments (up to 1 month will be allowed for the final 6-month assessment), though attempts will be made to complete them as close as possible (+/- 3 days) to the due date.

5. Flexibility. Follow-up visits may be completed by telephone and may occur during evening or weekend hours. This will make it easier for participants to schedule and complete their assessments, without requiring them to travel to a research site.

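### Section 14.1 states a hotline flag and phone attempt after a repeat overdose visit for the SDC arm only; one research-contact rule should cover both arms

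*Combined protocol and SAP*

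**What the plan says.** Section 14.1 (Data Collection and Management Responsibilities) provides for a list of SDC participants, and no others, to go to the hotline call center. The reason given is that "there is not a study RA on call 24/7", so the call center needs its own way of knowing not to send a peer to someone in the SDC arm. The section limits the scope: "This will only be relevant in the rare instances for which a study participant in the SDC arm has a repeat overdose visit" to a study ED and the hotline is called. In those cases an RA is to make an unscheduled or follow-up visit, with a reference to Section 7.3, "in the ED once available (if the participant remains in the ED) or will attempt to follow up by phone".

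Section 7.3.5 (Unscheduled Visits) holds the general rule, in a paragraph that begins "Participants in both the SDC and Relay intervention arms will be given a study phone number". After a repeat overdose with hotline activation, "RAs will attempt to visit the participant in the ED if possible (e.g., if an RA is available"). The purpose is to confirm contact details and appointments, "or to conduct one of the scheduled intermediate or final study visits if within the appropriate time window". No phone attempt is mentioned.

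The retention plan in 5.4.1 has no arm restriction. It says "we will monitor ED visits to study hospitals made by patients subsequent to the baseline visit", and "Follow-up visits may be completed by telephone and may occur during evening or weekend hours".

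Under 4.2.2, self-reported overdose comes from the 1-, 3- and 6-month visits, and time to next overdose is also self-reported. Under 10.4.2, ED visits and fatal overdoses in the primary count come from administrative data. Other non-fatal overdoses come from interviews through six months and are estimated for the second half-year.

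**The concern.** A repeat overdose is itself an outcome event. If it prompts extra research contact in one arm only, the chance that a person's self-report is obtained depends jointly on arm and outcome. SDC participants who overdosed could then be over-represented among completed SDC interviews, and Relay would look better with no true effect. An apparent benefit on self-reported overdose or time to next overdose would be open to that explanation. Any excess in the self-reported part of the primary count could also carry into the months that are estimated rather than observed.

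An RA acting on an SDC-only list may also learn the arm, although 10.6.1 tries to keep follow-up interviewers blinded where possible.

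**Working it through.** The plan gives no figure on this point, so there is none to reproduce. The check sets the rules side by side and then bounds the size on stated assumptions.

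**1. The two rules after a hotline-activated repeat overdose at a study ED**

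| | SDC | Relay |
|---|---|---|
| ED visit by an RA | Yes, if one becomes available and the patient is still there | Attempted, if one is available |
| Flag at the hotline when no RA is on call | Yes (14.1) | None stated |
| Phone attempt tied to the event | Yes (14.1) | None stated |
| General ED monitoring, phone visits, repeated attempts (5.4.1) | Yes | Yes |

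The documented difference is the second and third rows. RA availability limits the ED visit in both arms.

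**2. When a contact can yield outcome data**

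The visit windows in 7.3.2 and 7.3.3 are days 23–44, 76–120 and 166–210. That is 22 + 45 + 45 = 112 of the first 210 days, or 53%. Outside a window, the contact refreshes locator details and appointments, which can still help a later interview.

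**3. Size for self-reported overdose**

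Inputs:
- True share with an overdose, p = 0.20 in both arms. Section 2.1 cites about 20% over 12 months in another trial; using it here is an assumption.
- Interview completion r0 = 0.70 without the extra contact and r1 = 0.85 with it (assumed).
- Share of events when no RA is on call, off = 0.5 (assumed).
- Share of overdosers with a hotline-activated visit at a study ED, h (assumed, varied).

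Formulas:
- Completion among SDC overdosers: rs = r0 + h × off × (r1 − r0)
- Observed SDC prevalence: p × rs / (p × rs + (1 − p) × r0)
- Spurious risk ratio: 0.20 / observed SDC prevalence, with Relay unchanged at 0.20

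| h | rs | SDC prevalence | Risk ratio |
|---|---|---|---|
| 1.00 | 0.775 | 0.155/0.715 = 21.7% | 0.92 |
| 0.50 | 0.7375 | 0.1475/0.7075 = 20.8% | 0.96 |
| 0.25 | 0.719 | 0.14375/0.70375 = 20.4% | 0.98 |
| 0.10 | 0.7075 | 0.1415/0.7015 = 20.2% | 0.99 |

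Varying the other inputs at h = 1 gives 0.95 (r0 = 0.80, r1 = 0.90, off = 0.5) and 0.87 (r0 = 0.70, r1 = 0.90, off = 0.7). At h = 0.5 the same two sets give 0.98 (0.20 ÷ (0.165/0.805)) and 0.93 (0.20 ÷ (0.154/0.714)).

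**4. Size for the primary count**

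Take a true incidence rate ratio of 1, with 2.0 events per person-year and overdispersion 1.6 (both from 10.5) and 175 per arm (350/2). Let f be the share of counted events known only by self-report, and g the relative excess capture of those events in SDC. Both are assumptions. The apparent rate ratio is 1/(1 + f × g), with standard error of its log √(1.6 × (1/(175 × 2(1 + fg)) + 1/(175 × 2))).

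| f | g | Apparent IRR, Relay/SDC | Two-sided type I error |
|---|---|---|---|
| 10% | 5% | 0.995 | 5.0% |
| 20% | 10% | 0.98 | 5.5% |
| 40% | 20% | 0.93 | 13.0% |

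If g is taken as rs/r0 − 1 from step 3, h = 0.5 with the central inputs gives 0.7375/0.70 − 1 = 5%. A g of 20% needs the most extreme set there, with h = 1 (0.84/0.70 − 1).

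**The case against.** The strongest reply is that both arms are followed in much the same way. Section 5.4.1 monitors repeat ED visits to study hospitals through Epic track boards and health-information-exchange alerts, with no arm restriction. Section 5.4.3 repeats the track-board monitoring for the two NYU EDs. Everyone can be interviewed by phone, and everyone gets multiple contact attempts and wide windows. Section 14.1 itself refers to Section 7.3 and calls the situation rare. The triggering event is an ED visit, so it enters the primary count administratively whatever the RA does.

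Most of this stands, and it limits the size. It does not remove the difference. The general tools make a repeat ED visit an opportunity for follow-up; they do not call for contact after an overdose. The reference to Section 7.3 attaches to the type of visit, and the repeat-overdose rule there contains no phone attempt. Rarity is asserted, not shown: Section 10.5 expects 2–3 opioid-related adverse events per person-year in SDC, although an unknown part of these are hotline-activated overdoses at study EDs.

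A reader might infer more: that RA availability limits contact for Relay participants only, or that outcomes will in fact be captured more fully in SDC. The documents support neither. The availability condition in 7.3.5 covers both arms, and the SDC visit in 14.1 also needs an available RA and a patient still in the ED. Whether an extra phone attempt raises completion is not known.

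**Conclusion.** The plan states a research contact that is triggered by an outcome event and written for one arm only. That is an avoidable source of differential ascertainment, and its likely direction favours Relay. It bears on self-reported overdose, time to next overdose, and the self-reported non-ED overdoses in the primary count. The self-reported secondary endpoints are more exposed than the primary endpoint, whose ED-visit and death components are unaffected.

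The size is unknown and probably small. On the central assumptions the spurious risk ratio for self-reported overdose is about 0.96 if half of overdosers have a hotline-activated study-ED visit, and 0.98 if a quarter do. A value of 0.92 requires every overdoser to have such a visit, which nothing in the plan supports. For the primary count the distortion is negligible at the low end of the range (0.995). It reaches 0.93 only if 40% of events rest on self-report alone and SDC captures 20% more of them. Completion rates, off-hours share, hotline share and the self-report share are all assumptions. The change is worth making because it is cheap, not because bias has been shown.

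**What to change.** State one repeat-overdose research-contact rule in 7.3.5 and have 14.1 refer to it. Preferably, extend to Relay participants the RA visit or phone attempt that 14.1 gives SDC participants, triggered from the hotline call record or the Relay program record. The SDC list can stay with the call center for its present purpose of preventing crossover. The alternative is to restrict both arms to the 7.3.5 rule, but that gives up retention contacts in a population that is hard to reach.

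Add a REDCap field that marks contacts and interviews prompted by a repeat overdose, and report contact attempts and visit completion by arm at 1, 3 and 6 months.

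An analysis that leaves out triggered interviews is not advised. It would selectively remove people who had just overdosed and, under the present rule, would remove more of them from SDC, including some who would have completed the visit anyway.

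The cost is a sentence or two of text, one data field, and a few more Relay-arm contacts.
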